6.1.2. Definition of Baseline and Postbaseline Measures

The baseline value for the efficacy (except flare), health outcomes is defined as the last non-missing measurement on or prior to the date of first study baricitinib administration. For patients who participate in the Safety/PK period, this value will be recorded on or before Visit 2 (Day 1); for the other patients who started with the OLLI period, this value will be recorded on or before Visit 5 (Week 0).

The baseline value for disease flare analyses is defined as the last non-missing measurement on or prior to the date of randomization (beginning of the DBW period). This value will be recorded on or before Visit 9 (Week 12).

Baseline for the safety analyses is defined in Section 6.18. Postbaseline measurements are collected after study drug administration through Visit 17 (Week 44) or early discontinuation visit. For data collected in the electronic Clinical Outcomes Assessment (eCOA) tablet (including Patient-Reported Outcomes [PRO] and Clinician-Reported Outcomes [ClinRO]) and related to efficacy assessments, unscheduled postbaseline visits that fall within the visit windows defined by Lilly will be summarized in the by-visit analyses if there is no scheduled visit available. Refer to clinical protocol I4V-MC-JAHV(d) for detail of the visit windows. If there is more than 1 unscheduled visit within the defined visit window and no scheduled visit is available, the unscheduled visit closest to the scheduled visit date will be used. If 2 unscheduled visits of equal distance are available, then the latter of the 2 will be used.

Postbaseline measures for the safety analyses are defined as the nonmissing scheduled (planned) measurements after the date of first study drug administration for continuous measures by-visit analyses and all nonmissing measurements after the date of first study drug administration for all other analyses.

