In the DBW period, the main analysis for all continuous efficacy and health outcomes variables will use analysis of covariance (ANCOVA) model with treatment, JIA patient categories (polyarticular and extended oligoarticular [combined] versus ERA and JPsA [combined]), predose exposure ESR categories (elevated [>20 mm/hour] and not elevated), history of prior bDMARD use (Yes or No), and baseline score as covariates in the model. For ESR and high-sensitivity C-reactive protein (hsCRP) analysis, predose ESR level categories will not be included as a covariate. Type III sums of squares for the least-squares mean (LSM) will be used for the statistical comparison of treatment groups, and the LSM difference, standard error, p-value and 95% CI will also be reported. The LOCF approach will be used to impute missing data.

The mixed model repeated measures (MMRM) analysis will also be considered as a supplemental analysis method. The MMRM will use a restricted maximum likelihood (REML) estimation. The model will include treatment, JIA patient categories (polyarticular and extended oligoarticular [combined] versus ERA and JPsA [combined]), predose exposure ESR categories (elevated [>20 mm/hour] and not elevated), history of prior bDMARD use (Yes or No), visit, treatment-by-visit-interaction, baseline score and baseline-by-visit-interaction as fixed effects. If any of these are redundant for a particular model, they will be dropped. An unstructured (co)variance structure will be used to model the between- and within-patient errors. If this analysis fails to converge, the heterogeneous autoregressive [ARH(1)], followed by the heterogeneous compound symmetry (CSH), followed by the heterogeneous Toeplitz (TOEPH) will be used. The Kenward-Roger method will be used to estimate the degrees of freedom. Type III tests for the LSM will be used for the statistical comparison. The LSM difference, standard error, p-value, and 95% CI will also be reported.

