6.2. Adjustments for Covariates

The randomization to treatment groups at Week 12 (Visit 9) is stratified by:

- history of prior bDMARD use (Yes versus No)
- the JIA categories
 - polyarticular and extended oligoarticular [combined] or
 - enthesitis-related JIA and JPsA [combined]
- predose exposure ESR categories (elevated [>20 mm/hour] and not elevated) in the polyarticular JIA patients

Unless otherwise specified, the statistical analysis models will adjust for JIA patient category (polyarticular and extended oligoarticular versus ERA and JPsA), history of prior bDMARD use (Yes or No), and predose exposure ESR categories (above 20 mm/L or below 20 mm/L). If any of these are redundant for a particular model, they will be dropped. The covariates used in the ANCOVA model for continuous data generally will include the parameter value at baseline. When an MMRM analysis is performed, baseline value and baseline-by-visit interactions will be included as covariates.

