6.3.1. Last Observation Carried Forward (LOCF)

According to ICH E9 R1, the while-on-treatment strategy could be applied based on the last postbaseline value at or before the visit of interest while the patient was still on study drug. The primary endpoint for efficacy evaluation, time to disease flare, is an endpoint that reflects loss of

treatment effect. Therefore, for patients who completed DBW via flare, the LOCF values appropriately estimate their disease status at this time and beyond.

All continuous endpoints will be imputed using the LOCF methodology after applying the censoring rule to those who discontinued study drug. For patients who permanently discontinue study treatment or discontinue from the study for any reason at any time, the last nonmissing postbaseline observation on or prior to discontinuation will be carried forward to subsequent time points for evaluation. LOCF will not be applied across OLLI and DBW analysis periods.

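### Double-blind comparisons of continuous endpoints adjust for the pre-baricitinib value but not for the Week 12 value at randomisation, which costs precision and leaves chance imbalance in the estimate

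*SAP*

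**What the plan says.** SAP 6.1.4 specifies ANCOVA as the main DBW analysis of all continuous efficacy and health outcome variables. Its terms are treatment, JIA category and predose ESR category, followed by "history of prior bDMARD use (Yes or No), and baseline score as covariates in the model". SAP 6.2 repeats the rule: "The covariates used in the ANCOVA model for continuous data generally will include the parameter value at baseline". For the supplementary MMRM it states that "baseline value and baseline-by-visit interactions will be included as covariates".

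SAP 6.1.2 gives two meanings of baseline. For efficacy other than flare, and for health outcomes, it is the "last non-missing measurement on or prior to the date of first study baricitinib administration", that is, Visit 2 or Visit 5. For flare alone: "The baseline value for disease flare analyses is defined as the last non-missing measurement on or prior to the date of randomization".

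On timing, SAP 6.2 says: "The randomization to treatment groups at Week 12 (Visit 9) is stratified by" three factors, namely prior bDMARD use, JIA category and predose ESR category. SAP 6.3.1 adds that "LOCF will not be applied across OLLI and DBW analysis periods". SAP Table JAHV.6.5 applies the DBW models to Weeks 16 to 44.

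**The concern.** The comparison is randomised at Week 12, so the natural covariate is the outcome's own value at Week 12. The plan instead adjusts for a value taken about 12 weeks earlier (about 14 for the Safety/PK cohort), before the open-label response. Everyone randomised has at least a PedACR30 response, but responses can run up to PedACR100, so disease activity at randomisation still varies. The other covariates are all fixed before baricitinib and do not stand in for it. The Week 12 value does not enter as an outcome row, because the models start at Week 16, nor through carry-forward, because LOCF stops at the period boundary.

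At stake are the intervals and p-values for the core-set components, JADAS-27, the CHQ-PF50 summary and caregiver scales, and CHAQ pain. The trial is sized for time to flare, so no power is reserved for these endpoints.

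**Working it through.** **The plan's own figure.** The only stated power is for time to flare: 128 patients (64 per arm), flare in 35% versus 60%, at most 10% dropout, two-sided 0.05, about 80% power (Protocol 10.1, SAP 5.2). Under exponential times, HR = ln(0.65)/ln(0.40) = 0.470. Events = 128 × 0.9 × 0.475 = 54.7. Schoenfeld power = Φ(|ln 0.470| × √54.7 / 2 − 1.96) = 79.7%. The figure reproduces, and 64 per arm is used below. No figure is stated for continuous endpoints.

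**Assumptions.** The documents give no correlations. Let a = corr(Week 0, DBW outcome), b = corr(Week 12, DBW outcome) and c = corr(Week 0, Week 12), in standardised units and the same in both arms. The stratification factors are left out.

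**Residual variance.**
- Week 0 only: 1 − a².
- Week 0 and Week 12: 1 − (a² + b² − 2abc)/(1 − c²).

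**Central case (0.3, 0.6, 0.4).**
- Week 0 only: 1 − 0.09 = 0.91.
- Both: 1 − (0.09 + 0.36 − 0.144)/0.84 = 0.636.
- Variance ratio 0.636/0.91 = 0.699; SE ratio √0.699 = 0.836, so the interval is 16% narrower.
- Equivalent sample size 1/0.699 = 1.43, or 43% more patients. Equally, 128 × 0.699 = 89 patients would give the planned precision.

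**Range.**

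| a | b | c | Variance ratio | CI narrower by | Equivalent extra patients |
|---|---|---|---|---|---|
| 0.3 | 0.6 | 0.4 | 0.699 | 16% | 43% |
| 0.3 | 0.5 | 0.5 | 0.821 | 9% | 22% |
| 0.2 | 0.5 | 0.3 | 0.778 | 12% | 28% |
| 0.4 | 0.7 | 0.5 | 0.603 | 22% | 66% |
| 0.4 | 0.4 | 0.5 (least gain) | 0.937 | 3% | 7% |
| 0.2 | 0.7 | 0.5 (most gain) | 0.500 | 29% | 100% |

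The last two rows are the extremes of a grid with a from 0.2 to 0.4, b from 0.4 to 0.7 and c at 0.3 or 0.5. A contrast with 80% power under the planned model would have Φ((1.96 + 0.842)/√ratio − 1.96): 91.8% in the central case, and 82.5% to 97.7% across the grid.

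**Chance imbalance.** With 64 per arm, the SD of the between-arm difference in Week 12 means is √(2/64) = 0.177 SD. Given Week 0 it is 0.177 × √(1 − 0.16) = 0.162. The Week 12 slope is (0.6 − 0.3 × 0.4)/(1 − 0.16) = 0.571. A one-SD imbalance therefore moves the planned estimate by 0.571 × 0.162 = 0.093 SD; across the grid the shift is 0.04 to 0.12 SD.

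**How the two losses relate.** The planned estimate has variance 0.91 × 2/64 = 0.0284. With Week 12 added it is 0.636 × 2/64 = 0.0199. The difference, about 0.0086, equals 0.093². The extra variance is the uncorrected imbalance.

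**Simulation check.** In 4,000 null trials of 64 per arm at the central correlations, the SD of the estimate was 0.170 with Week 0 only and 0.142 with both. Both estimators averaged about zero. The correlation of the estimate with the Week 12 imbalance was 0.51 with Week 0 only and 0.01 with both.

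**The case against.** The strongest reply is that nothing here is invalid, and most of that reply stands. Randomisation keeps the planned ANCOVA unbiased on average. The primary endpoint is untouched and already uses Visit 9 as its reference. The affected analyses are secondary or supplementary, with no multiplicity control. Precision and imbalance should be counted once, as the variance identity shows: the planned interval is wider but already covers the random imbalance.

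The size is also open to challenge. The correlations are assumed. Restricting randomisation to responders may compress the Week 12 range. With 60% of placebo patients expected to flare and flare-visit values carried forward, the Week 12 correlation may be weaker in that arm. A gain of only 3% is possible. The models also adjust for JIA category, predose ESR category and prior bDMARD use, so the criticism concerns the outcome's own earlier value, not all covariates.

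Finally, a pre-treatment reference is coherent: it keeps change scores comparable between the open-label and blinded periods, and the protocol also names only a baseline score. That supports reporting change from Week 0. It is no reason to leave the Week 12 value out of the model, since change from Week 0 can remain the outcome with both values as covariates. None of these points identifies a material cost of adding the covariate.

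**Conclusion.** The concern holds. The DBW ANCOVA and MMRM for continuous endpoints leave out the outcome's value at randomisation, although it precedes treatment assignment and the SAP already uses it for flare. The cost is wider intervals and estimates that move with chance imbalance at Week 12, not average bias. The central estimate is an interval 16% wider than it would be relative to the planned width, with a range of 3% to 29%. Both rest on assumed correlations, a common correlation structure in the two arms, 64 patients per arm and no allowance for the stratification factors. The reading of the text is firm; the exact size is not. This should be changed as an inexpensive improvement to the secondary inference. It does not threaten the primary result.

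**What to change.** In SAP 6.1.4 and 6.2, add to the DBW ANCOVA the endpoint's last non-missing value on or before randomisation (Visit 9), alongside the existing Week 0 value. In the MMRM, add it with its interaction with visit. Apply this to every continuous DBW endpoint that is compared between arms with these models and measured at Visit 9. Change from Week 0 can stay as the reported outcome.

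PASI, SPARCC and JSpADA need no change because SAP Table JAHV.6.9 plans summaries only. The mTSS analysis has its own ANCOVA in SAP 6.11.1 and is outside this point.

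The cost is one covariate, about one degree of freedom per ANCOVA, and no new data collection: the core-set values at Visit 9 already decide PedACR30 entry and serve as the flare reference. The treatment contrast in these linear models is unchanged. Protocol 10.3.1 lists the covariates without this one, so the departure and its reason belong in the clinical study report, as that section requires. The change should be fixed before treatment codes are opened.

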6.3.3. Mixed Model for Repeated Measures (MMRM)

An MMRM method can be justified based on the hypothetical strategy (ICH E9 R1) for handling intercurrent events. In this strategy the effect of study treatment is assessed in a hypothetical trial where all patients have complete data and continue to take study treatment without dropping out of the study. The MMRM method assumes that missing data can bias results, but the bias can be attenuated by modeling random effects using the within-subject error correlation structure. These correlations between the repeated measurements provide the platform used to account for the bias from subject dropout by assuming the dropout follows missing at random (MAR) assumption.

Selected efficacy and health outcomes variables will be assessed using MMRM as a supplementary analysis. The details are described in [Table JAHV.6.5](#).

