Measure	Variable	Population	Analysis Timepoint	Treatment Comparisons	Analysis Method	Analysis Type
Disease flare	Proportion of patients with disease flare	DBW	Week 16 to Week 44	Baricitinib versus placebo	Logistic regression	Secondary analysis
PedACR response	PedACR30/50/70/90/100 response rates (compare to patient's condition prior to first dose of investigational product)	Safety/PK, OLLI, OLLI2	Week 2 to Week 12	No comparison	Summary statistics	Secondary analysis
		DBW	Week 16 to Week 44	Baricitinib versus placebo	Logistic regression	Secondary analysis
Active joint count	Change from baseline of active joint count	OLLI2	Week 2 to Week 12	No comparison	Summary statistics	Secondary analysis
		DBW	Week 16 to Week 44	Baricitinib versus placebo	ANCOVA MMRM	Secondary analysis Supplementary analysis
Limited of range motion joint count	Change from baseline of limited range of motion joint count	OLLI2	Week 2 to Week 12	No comparison	Summary statistics	Secondary analysis
		DBW	Week 16 to Week 44	Baricitinib versus placebo	ANCOVA MMRM	Secondary analysis Supplementary analysis
Physician's global assessment of disease activity	Change from baseline of physician's global assessment of disease activity	OLLI2	Week 2 to Week 12	No comparison	Summary statistics	Secondary analysis
		DBW	Week 16 to Week 44	Baricitinib versus placebo	ANCOVA MMRM	Secondary analysis Supplementary analysis
Physical function as measured by CHAQ	Change from baseline of physical function	OLLI2	Week 2 to Week 12	No comparison	Summary statistics	Secondary analysis
		DBW	Week 16 to Week 44	Baricitinib versus placebo	ANCOVA MMRM	Secondary analysis Supplementary analysis

Description of Analysis Period and Analysis Method of Secondary Endpoint and Health Outcome

Measure	Variable	Population	Analysis Timepoint	Treatment Comparisons	Analysis Method	Analysis Type
Parent's global assessment of overall well-being as measured by CHAQ	Change from baseline of parent's global assessment of overall well-being	OLLI2	Week 2 to Week 12	No comparison	Summary statistics	Secondary analysis
		DBW	Week 16 to Week 44	Baricitinib versus placebo	ANCOVA	Secondary analysis
					MMRM	Supplementary analysis

Description of Analysis Period and Analysis Method of Secondary Endpoint and Health Outcome

Measure	Variable	Population	Analysis Timepoint	Treatment Comparisons	Analysis Method	Analysis Type
hsCRP (mg/L)	Change from baseline of hsCRP	OLLI2	Week 2 to Week 12	No comparison	Summary statistics	Secondary analysis

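### The MMRM covariance fallbacks in SAP 6.1.4 put heterogeneous Toeplitz last, behind two of its own special cases, so if the unstructured fit failed the supplementary Week 44 estimates would rest on ARH(1)

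*SAP*

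**What the plan says.** SAP 6.1.4 gives MMRM a secondary role: "The mixed model repeated measures (MMRM) analysis will also be considered as a supplemental analysis method". The main analysis of continuous endpoints in the double-blind withdrawal (DBW) period is ANCOVA, for which "The LOCF approach will be used to impute missing data".

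For the MMRM, "An unstructured (co)variance structure will be used to model the between- and within-patient errors". If that does not converge, "the heterogeneous autoregressive [ARH(1)], followed by the heterogeneous compound symmetry (CSH), followed by the heterogeneous Toeplitz (TOEPH) will be used". On inference, "The Kenward-Roger method will be used to estimate the degrees of freedom". No fit criterion, robust standard error or sensitivity to the chosen structure is specified.

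SAP 6.3.3 presents MMRM as the hypothetical-strategy analysis, takes exits to be MAR, and states what the correlations are for: "These correlations between the repeated measurements provide the platform used to account for the bias from subject dropout".

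Table JAHV.6.5 lists MMRM as supplementary for six measures over "Week 16 to Week 44": active joints, joints with limited motion, physician global, CHAQ function, parent global and JADAS-27. Table JAHV.6.7 adds the hsCRP version of JADAS-27 at fewer visits.

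**The concern.** A fallback list normally gives up flexibility step by step, so that each move discards as little as possible. This list drops from the most general structure straight to one of the two most restrictive and puts the intermediate one last. Toeplitz is then reached only when two simpler versions of it have already failed, and at that point it is unlikely to succeed.

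The choice matters more here than in most trials. Flare ends participation (SAP 5.1), and data after permanent discontinuation of study drug are excluded (SAP 6.3). Exit is therefore frequent, driven by the outcome and planned to be unequal between arms. Under MAR the model fills the gap by carrying a child's last observed level forward through the fitted correlations. ARH(1) lets that information fade quickly, so a child who left with a high score is predicted to drift back to the arm mean.

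MMRM is there to show whether the LOCF results hold under a different missing-data assumption. If a restrictive covariance moves the estimate, a gap between the two analyses could be misread as a missing-data effect.

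**Working it through.** **Inputs from the documents.** Eight DBW visits: Weeks 16, 20, 24, 28, 32, 36, 40 and 44. 64 patients per arm, flare 35% on baricitinib and 60% on placebo, dropout at most 10%, two-sided 5% level (SAP 5.2). The documents give no SD and no between-visit correlation, so these are assumed below and varied.

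**The plan's own figure.** The exit rates come from the sample-size assumptions, which reproduce. With exponential times, HR = ln(0.65)/ln(0.40) = 0.470. The Schoenfeld formula needs 56 events for 80% power. Mean flare is (0.35 + 0.60)/2 = 0.475, so N = 56/0.475 = 118, and 118/0.9 = 131, close to 128. With 128 × 0.9 × 0.475 = 54.7 events, power is 79.7%. The plan states no figure for the MMRM.

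**Nesting.** Covariance parameters for 8 visits:

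- Unstructured: 8 × 9/2 = 36
- Toeplitz (heterogeneous): 8 variances + 7 lag correlations = 15
- ARH(1): 8 + 1 = 9
- CSH: 8 + 1 = 9

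Setting the seven lag correlations to rho^k gives ARH(1); setting them all equal gives CSH. Both are special cases of Toeplitz.

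**What ARH(1) imposes.** A lag-1 correlation of 0.6 implies 0.6^7 = 0.028 between Week 16 and Week 44.

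**Large-sample bias.** Simulation with 100,000 per arm, SD 1 and flare exit depending on the observed score at that visit (MAR), calibrated to about 35% and 59% flare with about 10% other dropout; REML fits. About 60% of baricitinib and 39% of placebo patients are still observed at Week 44. Bias in the Week 44 difference (true value 0.70 to 0.72 SD):

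| Assumed true correlation | ARH(1) | CSH | Toeplitz | Unstructured |
|---|---|---|---|---|
| Intercept plus AR, lag 7 = 0.48 | -15.0% | +1.7% | -0.3% | -0.4% |
| Intercept plus AR, lag 7 = 0.34 | -12.6% | +2.0% | -0.5% | -0.6% |
| Constant 0.6 | -23.1% | +0.1% | +0.1% | 0.0% |
| AR(1), lag 1 = 0.8 | -1.0% | +3.3% | -1.0% | -1.0% |

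The first row shows the mechanism. With true Week 44 means of 0 (baricitinib) and 0.717 (placebo), ARH(1) returns -0.173 and 0.437. Both are too low, placebo by more (0.280 against 0.173), because more placebo children left with high scores. The difference shrinks from 0.717 to about 0.61.

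**Sensitivity to the assumed settings.**

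- One alternative (ML, 120,000 per arm): ARH(1) -9.6%, -7.0% and -4.3% under constant, mixed and slowly decaying correlation, against -0.1%, -1.3% and +0.4% with Toeplitz; -1.2% for each under true AR(1).
- Another (ML): ARH(1) -41% under constant correlation 0.6, -26% under mixed correlation and +0.7% to +2.1% under true AR(1), against 2% or less in size with Toeplitz. CSH ran from -0.7% to +14%.
- An exit rule closer to the real flare definition (at least 3 of 6 components crossing a threshold) reduced the ARH(1) bias but did not remove it.

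**At trial size.** 64 per arm, 150 runs, t cut-off 1.97 in place of Kenward-Roger:

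| Pattern | Fit | Mean bias | 95% CI coverage | Power |
|---|---|---|---|---|
| Intercept plus AR (lag 7 = 0.48) | ARH(1) | -16.9% | 93% | 73% |
| | Toeplitz | -4.3% | 95% | 85% |
| Constant 0.6 | ARH(1) | -23.3% | 89% | 67% |
| | Toeplitz | -3.5% | 97% | 89% |

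The Monte Carlo standard error of the Toeplitz bias in the first pattern is 0.218/√150 = 0.018, or 2.5% of 0.717, so -4.3% is within two standard errors of zero. For coverage it is √(0.95 × 0.05/150) = 1.8 points. Thus 93% is not distinguishable from 95%, while 89% is.

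**The case against.** **The trigger may never be pulled.** The sequence applies only if the unstructured fit fails. A reader might infer that failure is likely, since only about 0.39 × 64 = 25 placebo patients remain at Week 44. But SAP 6.1.4 does not specify a separate covariance for each arm, so the usual reading is one matrix pooled over both, with about 0.60 × 64 + 0.39 × 64 = 63 patients. In 80 simulated trials of 64 per arm with these exit rates, the unstructured fit converged every time, with at least 47 patients at Week 44. Those fits used ML, Gaussian data and no stratification covariates, so skewed joint counts could behave worse. The documents give no sign that the fit will fail. This objection stands and limits the point.

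**No main result depends on it.** A reader might take a biased Week 44 difference to mean a biased efficacy finding. The documents do not support that: the primary analysis is the stratified log-rank test, the main continuous analysis is ANCOVA with LOCF, and the sample size does not involve MMRM. Nor is the bias in the drug's favour; wherever correlation persisted it ran towards zero.

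**The order is prespecified and conventional.** There is no post-hoc choice, simple-first is a recognised habit in small samples, and decay is natural for visits four weeks apart. All true, but none of it is a reason to place Toeplitz last, because moving it forward leaves the simple structures available.

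**CSH might belong ahead of ARH(1).** Some settings favour this (CSH within about 4%), but another gave CSH bias up to +14%. Each is biased when the other's pattern is true, so no order of the two is established.

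**Fewer visits for one measure.** If only Weeks 16, 32 and 44 enter the model for the hsCRP version of JADAS-27, unstructured has 6 parameters and Toeplitz 5, and the issue nearly vanishes there.

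**Conclusion.** The point holds as a minor, conditional one. The ordering makes the only flexible fallback practically unreachable; that follows from the nesting and needs no simulation.

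The consequence requires two things: the unstructured fit fails, and correlation truly persists across visits. The supplementary Week 44 differences would then be pulled towards zero. Across assumed large-sample scenarios the size is about -4% to -40%, against about 2% or less in size with Toeplitz. If the truth is AR(1), the two agree and the bias is about nil. No single figure in that range should be quoted as the expected bias, because it depends on correlations, effect size and exit rule that the documents do not supply. Kenward-Roger adjusts inference under the fitted structure and does not repair the estimate.

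Toeplitz would not remove every source of bias. Flare is judged against Visit 9, whereas the baseline for these endpoints is before the first baricitinib dose (SAP 6.1.2). Exit may therefore depend on a value outside the model, whichever structure is used.

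**What to change.** In SAP 6.1.4, make heterogeneous Toeplitz the first fallback after unstructured, and keep ARH(1) and CSH as later backstops, using the first structure that converges. The order of the last two is a matter of judgement.

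Two small additions would help: report which structure was used for each measure, and, if ARH(1) or CSH is reached, give a sandwich standard error in place of the Kenward-Roger one. The latter corrects the standard error, not the bias.

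The cost is one reordered sentence, made before unblinding. It needs no new data and loses no backstop; if Toeplitz fails, the same simple structures are still tried.
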